5.5.9 Concomitant treatment

The investigator should instruct the subject to notify the study site about any new medications he/she takes after the start of the study drug.

All prescription medications, over-the-counter drugs and significant non-drug therapies (including physical therapy and blood transfusions) administered or taken within the timeframe defined in the entry criteria prior to the start of the study and during the study, must be recorded on the Concomitant medications/ Significant non-drug therapies section of the CRF.

Medication entries should be specific to trade name, the single dose and unit, the frequency and route of administration, the start and discontinuation date and the reason for therapy.

5.5.10 Prohibited treatment

Use of the treatments displayed in the table below is NOT allowed after screening.

If, nevertheless, any of the below mentioned medication is taken during the study, a patient has either to be withdrawn from the study in case they are in the double-blind part or can stay in the study if they stop immediately the medication if such medication(s) have a short half-life or a minimal impact if taken punctually (see [Table 5-3](#)).

Commercially Confidential Information

Table 5-3 Prohibited treatment

Medication	Action
IVIg, plasmapheresis	Withdraw from double-blind period, unblind treatment and follow-up for safety
I.V. or oral cyclophosphamide	Withdraw from double-blind period, unblind treatment and follow-up for safety
Rituximab	Withdraw, unblind treatment and follow-up for safety. If taken after Week 24, patient should go directly to EOS visit.
Etanercept, adalimumab, ustekinumab, infliximab or any other immunologically active biologic therapy	Withdraw from double-blind period, unblind treatment and follow-up for safety
UVB/PUVA therapy	Discontinue phototherapy
Azathioprine, mycophenolate mofetil (if not part of SoC medication from Screening), dapsone, methotrexate, and any systemic immunosuppressants or immunomodulators	Discontinue medication
topical corticosteroids	Discontinue medication
topical calcineurin inhibitors (e.g., elidel)	

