3. Assessments to be conducted locally at Screening to confirm presence of pemphigus vulgaris (PV) only where not previously performed and documented as part of the patient's regular medical care.
4. Vital signs: Sitting blood pressure and heart rate measurement required at all visits, plus standing measurements only at Screening and Baseline. During study drug administration, blood pressure and heart rate should be obtained every 30 minutes.
5. For women, serum pregnancy testing (human chorionic gonadotropin, hCG) is required screening and end of study regardless of reported reproductive/menopausal status. Urine pregnancy test will be performed at Baseline (Day 1) and every post-dose visit from Week 3 onwards, and may be conducted in addition at the discretion of the investigator or may be required more frequently by local practices, if a menstrual cycle is missed, or if potential pregnancy is otherwise suspected.
6. For postmenopausal women, FSH conducted at Screening to assist in confirming menopausal status.
7. Administration: VAY736 infusion over 1-2 hours following premedication with paracetamol (or acetaminophen) and a H1 receptor blocker.
- 8.
9. Commercially Confidential Information
- 10.
- 11.
12. PK samples on Day 1 to be taken (1) pre-dose, (2) at the end of infusion when the indwelling line is empty and (3) 24 h post-dose (start of infusion: \pm 2 h).
13. Assessment completed by the investigator.
14. Assessment completed by the patient.
15. Commercially Confidential Information
16. At the selected sites (refer to footnote 15) this sample will be collected after Week 12 if the IGA score increases by at least 1 compared to the previous visit in patients that have previously reached disease control.
17. At Week 24 the blind will be broken and patients who were on placebo will be offered the opportunity to receive open label VAY736 administration at Week 25, and will follow the same visit pattern as if re-starting from Day 1. Refer to [Section 5.5.8](#) for unblinding prior to Week 24.

18. Serious adverse events are reportable from time of signing informed consent until 30 days after patient has stopped study participation. During the second part of the long-term safety follow-up (from Week 76), only AEs related to VAY736 and/or to infection, potential malignant events and neutropenia will be recorded.

19.

Commercially Confidential Information

20.

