5.4 Treatment blinding

This is a partial blind study: subjects, investigator staff, persons performing the assessments, and data analysts will remain blind to the identity of study treatments at the time of randomization and during the double-blind treatment period according to the specifications provided in [Appendix 4](#). Randomization data are kept strictly confidential until the time of unblinding for the respective person(s) with the following exceptions:

- The pharmacist charged with preparing and distributing infusion solutions containing VAY736 or placebo
- The medical monitor/Investigator at the site, independent to the study, who will review the hematology panel including differentials results throughout the study
- The unblinded monitor source data verifying the hematology panel and monitoring drug accountability

The PK bioanalyst will be unblinded during the clinical study, but will not provide individual PK data prior to data-base lock, except in case of an interim analysis happening after all patients have completed Week 24 and all team members, investigators and patients have been unblinded.

In order to help reduce the risk of unblinding that might arise if an infusion reaction occurs, all patients will receive treatment with paracetamol/acetaminophen and a H1 receptor blocker prior to infusion with VAY736.

An unblinded pharmacist at the investigator site will prepare the study treatment for infusion from the bulk open-labeled supplies. The diluent (dextrose 5% in water solution) serves as placebo and will not contain VAY736.

the hematology laboratory evaluation results will be concealed from the Investigators and patients in order to maintain the study blind. The necessary safety review may lead to the Novartis study team being inadvertently unblinded, however this information will not be communicated to the investigator.

Investigators and patients will be unblinded to treatment assignment after Week 24 (or earlier see [Section 5.5.8](#)) visit in order to propose open-label administration of VAY736 to the placebo arm.

Further unblinding will only occur in the case of subject emergencies (see [Section 5.5.12](#)), at the time of the interim analysis and at the conclusion of the study.

Further information regarding blinding (and unblinding) is presented in [Appendix 4](#).

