5.5.8 Rescue medication

Except the patient's Standard of Care treatment (SoC; oral corticosteroid +/- adjuvant therapy) described in [Section 5.5.5](#), no additional rescue medication is allowed; however, adjustment to a patient's SoC is allowable, with certain conditions, for a patient to remain on study.

During the Double-blind period (Weeks 0 to 24), adjustment of SoC is limited to one (1) increase (either corticosteroid or adjuvant therapy alone or both on the same day) in the first 24 weeks if the IGA score worsens by 1 point or more. With one increase, a patient can continue on the study without change to the study visit schedule.

If a patient has already had an increase in oral corticosteroid or in adjuvant immunosuppressive drugs (azathioprine or mycophenolate mofetil) and is still experiencing a disease flare up that in the Investigator's opinion requires intervention (e.g., IGA score worsens by a further 1 point or more from the prior SoC increase timepoint), then depending on when this second increase of SoC happens the patient should follow the schedule below:

- Second increase in SoC up to & including Week 12 – Patient to return and complete visits up to & including the Week 12 visit. Treatment to be unblinded early at the Week 12 visit.
- Second increase in SoC after Week 12 – Patient to return and skip forward to complete the Week 24 visit assessments. Treatment to be unblinded early (at the time of SoC increase or at the Week 24 visit).

Following this early unblinding, a patient on placebo is to be offered the opportunity of open label VAY736, whereas a patient on VAY736 would enter the long-term follow-up period (from Week 32 onwards). Similarly, if a patient previously on placebo prefers not to receive open label active treatment, they are to return within 4 weeks for their EoS visit

Commercially Confidential Information

If more than two increases of SoC treatment are required in an aim to control a patient's disease symptoms, such a patient will already have been withdrawn from the double-blind period and skipped forward to be monitored in the long-term follow up period following the second increase in SoC. Such patients would already have had their treatment unblinded after the second increase. These patients should continue to return for the visits/assessments in the long-term follow up period (from Week 32 onwards).

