Patients who withdraw prior to Week 12 should return for the Week 12 visit before skipping forward to enter the long term follow up period. Patients who withdraw after the Week 12 visit yet prior to Week 24 should return for the Week 24 visit before entering the long term follow up period (after Week 24). During the long term follow up period, patients will have visits according to the following schedule

until up to 2 years after last dose, Commercially Confidential Information unless the patient starts another immunomodulatory or immunosuppressive treatment:

- Every 8 weeks until the Week 40 visit
- A Week 52 visit
- Every 24 weeks until Week 100 visit

Commercially Confidential Information

The End of Study visit will include study completion evaluations followed by discharge from the study.

Patients who withdraw after Week 24, during the long term safety follow up period, will be asked to return and complete the end of study visit. Commercially Confidential Information

Commercially Confidential Information

For subjects who are lost to follow-up (i.e. those subjects whose status is unclear because they fail to appear for study visits without stating an intention to withdraw), the investigator should show "due diligence" by documenting in the source documents steps taken to contact the subject, e.g. dates of telephone calls, registered letters, etc.

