6.4 Efficacy / Pharmacodynamic assessments

6.4.1 Pemphigus Disease Area Index (PDAI)

The PDAI is a specific cutaneous and mucosal disease activity assessment performed by the investigator based on the evaluation of lesions in well-defined anatomical locations ([Pfützte et al 2007](#); [Murrell et al 2008](#); [Rosenbach et al 2009](#); [Daniel et al 2012](#)).

The score is weighted for the number and size of lesions with a score of 0 (absent) to 10 given for skin (12 body locations), scalp and mucous membrane showing disease activity (erosions/blisters or new erythema). To be more precise at the lower end of the PDAI score the value of 1 that included 1-3 lesions on each anatomic region is split in intervals: 1 corresponds to one lesion (none greater than 2 cm); 1.3 corresponds to two lesions and 1.6 corresponds to three lesions.

Damage, such as post inflammatory hyperpigmentation or erythema from resolving lesion, is scored separately from the main score as absent (0) or present (1) for each body area or scalp resulting in a score of 0 to 12 or 0 to 1, respectively.

Therefore the PDAI score ranges from 0 to 263, with 250 points representing disease activity (120 points for skin activity; 10 points for scalp activity; 120 points for mucosal activity) and 13 points representing disease damage. Please refer to the PDAI scoring sheet in [Section 18-Appendix 6](#).

The investigator will complete a paper copy of the scale, which will serve as source data and the subject's responses will be transcribed into the CRF.

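### Table 5-3 orders unblinding after four kinds of prohibited treatment without tying it to efficacy scoring, so a patient withdrawn before Week 12 may have the primary PDAI scored unblinded

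*Protocol*

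**What the plan says.** **Unblinding after prohibited treatment.** Protocol Section 5.5.10, Table 5-3, gives the same action for IVIg or plasmapheresis, for cyclophosphamide, and for etanercept, adalimumab and other immunologically active biologics: "Withdraw from double-blind period, unblind treatment and follow-up for safety". The rituximab row also orders withdrawal, unblinding and safety follow-up, but does not limit the withdrawal to the double-blind period. The remaining rows require only that the treatment stop, for example "Discontinue phototherapy".

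**Return visit.** Section 5.5.11: "Patients who withdraw prior to Week 12 should return for the Week 12 visit before skipping forward" to long-term follow-up.

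**Who scores.** Section 6.4.1: "The PDAI is a specific cutaneous and mucosal disease activity assessment performed by the investigator". The footnote to the assessment schedule for PDAI, IGA and ABSIS agrees: "Assessment completed by the investigator". No independent assessor is named.

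**Primary time point.** The synopsis, under Data analysis, places the primary comparison at Week 12.

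**Other rules on opening the code.** For a second increase in standard of care up to Week 12, Section 5.5.8 continues visits through Week 12 and states: "Treatment to be unblinded early at the Week 12 visit". Section 5.4 keeps assessors blind during the double-blind period and provides for unblinding after Week 24, or earlier under 5.5.8. It then adds: "Further unblinding will only occur in the case of subject emergencies", at interim analysis and at study end. Event 5 of Table 16-1 in Appendix 4 places unblinding of a single patient after Week 24, or at Week 12 under the 5.5.8 conditions.

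**The concern.** The PDAI is a clinician's lesion score, and the blind is its main protection against expectation. Taken together, Table 5-3 and Section 5.5.11 allow a sequence in which a patient takes a listed treatment before Week 12, is withdrawn, has the code opened, and is then scored at Week 12 by an investigator who knows the arm. No visible text rules this out.

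The placebo arm is planned at 6 patients, so one score carries one-sixth of that arm's mean. No visible text says how a PDAI scored after unblinding or after prohibited treatment is to be handled. The SAP section on supportive analyses (7.1.4) states that none apply.

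**Working it through.** **Step 1. The passages side by side, for a listed treatment taken before Week 12**

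| Source | What it implies |
|---|---|
| 5.5.10, Table 5-3 | Withdraw and unblind; no time stated, no link to scoring |
| 5.5.11 | Return for Week 12, then long-term follow-up |
| Section 6 (visit assessments) | After premature withdrawal, final-visit assessments as soon as possible |
| 5.4 | Assessors blind in the double-blind period; this route not listed |
| Appendix 4, event 5 | Single-patient unblinding after Week 24, or Week 12 under 5.5.8 only |
| 5.5.8 (second increase up to Week 12) | Code held until the Week 12 visit |

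A site cannot follow all of these. Opening the code before Week 12 fits Table 5-3 but not 5.4 or Appendix 4. Holding it fits those two, but Table 5-3 does not ask for it. The visit rules in 5.5.11 and Section 6 also differ.

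**Step 2. The plan's own operating characteristics**

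Inputs: 9 versus 6 patients and SD 8 (Section 9.6). The synopsis requires 50% posterior probability of a difference of at least 10 points and 90% posterior probability of any difference, with non-informative priors. I use a simple two-group comparison at Week 12.

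- SE = 8 × √(1/9 + 1/6) = 4.216
- The 50% criterion needs an observed difference of at least 10.
- The 90% criterion needs at least 1.2816 × 4.216 = 5.40, so the 10-point criterion governs.
- P(both met) = 1 − Φ((10 − d)/4.216), where d is the true difference.

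| True difference | Computed | Stated in 9.6 |
|---|---|---|
| 0 | 0.89% | below 1% |
| 6 | 17.1% | below 20% for differences under 6 |
| 14 | 82.9% | about 80% |

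The first two agree. The third is 2.9 points above the stated figure, and 80% is reached at a true difference of 13.55. This looks like conservative rounding and has no bearing on the point.

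**Step 3. Illustration of a scoring bias**

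The documents give neither the number of affected patients nor the size of any scoring bias; both are assumed. If one placebo score is b points too high, the observed difference shifts by b/6 and the false-positive chance is 1 − Φ((10 − b/6)/4.216).

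| b | Shift | False-positive chance |
|---|---|---|
| 0 | 0 | 0.9% |
| 5 | 0.83 | 1.5% |
| 10 | 1.67 | 2.4% |
| 15 | 2.50 | 3.8% |

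**Step 4. The opposite direction**

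Suppose instead that the prohibited drug lowers one placebo patient's Week 12 PDAI by 10 points (assumed). The shift is −10/6 = −1.67.

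- False-positive chance: 1 − Φ(11.67/4.216) = 0.3%
- Chance of success at a true difference of 14: 1 − Φ((10 − 12.33)/4.216) = 71%, against 82.9%

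**Step 5. Leaving the affected score out**

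- 9 versus 5: 1.25% false positive, 81.5% success at 14.
- 8 versus 6: 1.03% false positive, 82.3% success at 14.

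Repeating the contrast without one score therefore costs little precision, on the assumption that the omission itself is uninformative.

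**The case against.** **Timing.** Table 5-3 does not say that the code is opened at the moment of withdrawal. With 5.4 and Appendix 4, one can read the plan as having no routine unblinding before Week 12. This stands: a reader might infer that these patients are always scored unblinded, but the documents support only that they may be.

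**Direction.** A reader might also infer that affected patients have uncontrolled disease, are mostly on placebo, and so bias the result towards VAY736. The documents do not support this. Section 5.5.7 names IVIG for hypogammaglobulinaemia and plasmapheresis for lowering VAY736 concentration, and the latter can concern only treated patients. Section 1.1 describes rituximab as effective in this disease, so a prohibited drug may itself lower the score.

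**Section 5.5.8 as a model.** It is a partial one. After Week 12 it allows the code to be opened when standard of care is increased, so it does not protect Week 24. Even at Week 12 it does not put scoring before unblinding within the visit.

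**Redaction.** The primary model, part of the analysis-set text and part of the SAP's protocol-deviation table are blacked out. A rule excluding these scores could sit there, so it cannot be said that they enter the primary analysis.

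**Scope.** Four rows of one table are involved, and only use before Week 12 touches the primary time point, in a trial declared non-confirmatory and partial-blind. That limits the weight of the point. It does not remove the conflict between the passages.

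**Conclusion.** The point holds as a possibility that the plan leaves open. For four rows of Table 5-3, unblinding is not tied to efficacy scoring; the patient is recalled for Week 12; and the investigator scores. Sections 5.4, 5.5.8, 5.5.10, 5.5.11 and 6 and Appendix 4 do not agree and must be reconciled whatever the size of the effect.

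The range of 1.5% to 3.8% assumes exactly one affected placebo patient, a bias of 5 to 15 points towards VAY736, and no effect of the prohibited drug. Under the reverse assumption in Step 4 the effect is a loss of power. Neither is a forecast: net direction and size are unknown, and the documents give no expected rate of prohibited use. The case for acting rests on the low cost of closing the gap in a trial with 6 planned placebo patients.

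**What to change.** 1. **Table 5-3 and Section 5.5.11.** State that, unless the code is needed for the patient's care, PDAI, IGA and ABSIS are completed and signed before it is opened. For withdrawal before Week 12, state that the Week 12 scoring comes before unblinding, in line with the timing in 5.5.8 for that period.
2. **Section 5.4 and Table 16-1, event 5.** Add the Table 5-3 route to the listed unblinding occasions.
3. **Section 6.** Reconcile its as-soon-as-possible visit rule with the Week 12 return in 5.5.11.
4. **SAP (RAP module 3).** Flag any PDAI scored after unblinding or after prohibited treatment, state how the primary analysis handles it, and repeat the Week 12 contrast without those scores. This belongs in 7.1.4. It is a sensitivity analysis, because leaving out such patients is itself selective.

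Cost: a few sentences in the protocol, an entry in Table 16-1 and one additional model run. The downside is possibly one extra scoring at an unscheduled visit for a few patients. No extra staff are needed.

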5.5.11 Discontinuation of study treatment and premature subject withdrawal

Study “Stopping rules”

Commercially Confidential Information

However, infusion reactions (hypersensitivity, cytokine release, anaphylaxis) can occur with administration of biologics,

Commercially Confidential Information . Increased susceptibility to infection is also a potential risk with therapies targeting elements of the immune response. Thus for patients on active treatment, the following guidance and stopping rules are provided:

Dose limiting toxicities (DLTs) will be assessed according to the standardized toxicity grading scale, the NCI Common Toxicity Criteria for Adverse Events [NCI-CTCAE/v4.0, Reference <http://evs.nci.nih.gov/ftp1/CTCAE/About.html>]. Although the stopping criteria will not incorporate an absolute requirement for causality, the potential relationship between an adverse event and VAY736 will be evaluated carefully on a case-by-case basis.

Overall study:

The study will be stopped if any of the following criteria are met, and no further patient will be dosed pending a full safety review:

- Any treatment-related death
- Decrease in neutrophil count:
 - a. If any subject requires G-CSF or GM-CSF treatment for neutropenia, or
 - b. If two or more subjects manifest a persistent neutrophil count <500 cells/uL, or
 - c. If four or more subjects manifest a persistent neutrophil count <1000 cells/uL
- More than 1 infusion reaction of grade 3 severity of the NCI-CTCAE/v4.0 Criteria within the first 5 treated subjects and an incidence of >20% thereafter
- Any treatment-related, grade 3 toxicity of the NCI-CTCAE/v4.0 Criteria with the following exceptions:
 - Events of Special Interest, including infusion-related (hypersensitivity, cytokine release, anaphylaxis), decreased neutrophil or leukocyte counts not requiring treatment, and diagnostic procedures involving elective or non-urgent hospital admission
 - Disease Specific Events that are due to the patients underlying PV diagnosis
 - AE/SAEs unrelated to the experimental compound as assessed by the investigator or Novartis
- Clinically significant (according to the investigator) and study drug-related, persisting changes from baseline in vital signs, electrocardiograms, or medically relevant, persistent changes in laboratory parameters, which are not consistent with existing co-morbidities, in >1 patient within the first 5 treated subjects and an incidence of >20% thereafter
- It is indicated by the early safety review of the first 9 patients ([Section 3.1](#)). In the event of an unfavorable safety review, the study will not progress to dose further patients but the 9 patients will continue in the study until EoS as planned
- Other clinically significant changes or effects in the opinion of the Investigator or Sponsor that are deemed unsafe to continue dosing

In addition all blinded safety data, including events of special interest and disease specific events, will be evaluated by the Sponsor and PI continuously and at scheduled meetings. The study may be put on hold pending further data analysis, and the decision to adjust the dose or modify the pre-medication if the following criteria occur:

- The principal investigator or the Sponsor considers that the number and/or severity of AEs justify discontinuation of the study.
- Other clinically significant changes or effects in the opinion of the Investigator or Sponsor that are deemed unsafe to continue dosing.

The study can also be terminated at any time for any reason by Novartis. Should this be necessary, the Investigator will be informed of the procedures to be followed to assure that adequate consideration is given to the protection of the patient's interests. The Investigator will be responsible for informing IEC / IRB's of the early termination of the trial.

Individual subject withdrawal

Due to the single dose nature of the study, no individual treatment stopping rules are provided. Patients may voluntarily withdraw from the study for any reason at any time. They may be considered withdrawn if they state an intention to withdraw, fail to return for visits, or become lost to follow-up for any other reason.

If a patient withdrawal occurs for any reason, the investigator must make every effort to determine the primary reason for a patient's withdrawal from the study and record this information on the CRF.

Patients that become pregnant during the study should be followed up as per the assessment schedule. The investigator may determine whether any assessments should not be performed if they are considered to not be clinically appropriate, in conjunction with the patients' treating physician/obstetrician.

Patients who withdraw prior to Week 12 should return for the Week 12 visit before skipping forward to enter the long term follow up period. Patients who withdraw after the Week 12 visit yet prior to Week 24 should return for the Week 24 visit before entering the long term follow up period (after Week 24). During the long term follow up period, patients will have visits according to the following schedule

until up to 2 years after last dose, Commercially Confidential Information unless the patient starts another immunomodulatory or immunosuppressive treatment:

- Every 8 weeks until the Week 40 visit
- A Week 52 visit
- Every 24 weeks until Week 100 visit

Commercially Confidential Information

The End of Study visit will include study completion evaluations followed by discharge from the study.

Patients who withdraw after Week 24, during the long term safety follow up period, will be asked to return and complete the end of study visit. Commercially Confidential Information

Commercially Confidential Information

For subjects who are lost to follow-up (i.e. those subjects whose status is unclear because they fail to appear for study visits without stating an intention to withdraw), the investigator should show "due diligence" by documenting in the source documents steps taken to contact the subject, e.g. dates of telephone calls, registered letters, etc.

